Appendix 2: Response Evaluation Criteria in Solid Tumors (RECIST) version 1.1
Criteria for evaluating response in solid tumors

RECIST v.1.1* will be used in this study for assessment of tumor response. While either CT or MRI may be utilized, as per RECIST v.1.1, CT is the preferred imaging technique in this study.

[figure not shown]
* As published in the European Journal of Cancer:

[figure not shown]
E.A. Eisenhauer, P. Therasse, J. Bogaerts, L.H. Schwartz, D. Sargent, R. Ford, J. Dancey, S. Arbuck, S. Gwyther, M. Mooney, L. Rubinstein, L. Shankar, L. Dodd, R. Kaplan, D. Lacombe, J. Verweij. New response evaluation criteria in solid tumors: Revised RECIST guideline (version 1.1). Eur J Cancer. 2009 Jan;45(2):228-47

[figure not shown]
Appendix 3: Imaging and treatment after first radiologic evidence of disease progression. Table represents irRECIST

[figure not shown]
| | Clinically Stable | | Clinically Unstable | |
|---|---|--|---|---|
| | Imaging | Treatment | Imaging | Treatment |
| First radiologic evidence of disease progression by RECIST v.1.1 | Repeat imaging at \geq 4 weeks at site to confirm disease progression | May continue study treatment at the local site Investigator's discretion while awaiting confirmatory tumor imaging by site by irRECIST | Repeat imaging at \geq 4 weeks to confirm disease progression per physician discretion only | Discontinue treatment |
| Repeat tumor imaging confirms disease progression by irRECIST | No additional imaging required | Discontinue treatment (exception is possible upon consultation with Sponsor) | No additional imaging required | Not applied |
| Repeat tumor imaging shows stable disease or partial or complete response by irRECIST | Continue regularly scheduled assessments | Continue study treatment at the local site Investigator's discretion | Continue regularly scheduled assessments | May restart study treatment if condition has improved and/or clinically stable per local site Investigator's discretion |

[figure not shown]
Immune-Related Response Evaluation Criteria In Solid Tumors: irRECIST; Response criteria in solid tumors: RECIST.

[figure not shown]

[figure not shown]

| | |
|--|--|
| | |
| | |
| | |
| | |

Objectives	
Primary objective:
 
• To assess the efficacy -as determined by the clinical benefit rate (CBR) (total number of objective responses plus stable disease for at least 24 weeks) based on RECIST v.1.1- of MK3475 (pembrolizumab) in combination with eribulin in patients with HR-positive/HER2-negative MBC who have previously received an anthracycline and a taxane (for either early or advanced disease), unless contraindicated, and between one to two lines of chemotherapy in the metastatic setting. 
Secondary objectives:

	
• To determine the CBR based on RECIST v.1.1 in subjects with programmed death ligand-1 (PD-L1) positive tumors.• To determine the progression-free survival (PFS) based on RECIST v.1.1.• To determine the PFS based on RECIST v.1.1 in subjects with PD-L1 positive tumors.• To determine the overall survival (OS) (OS will be determined at the end of the study).• To determine the OS in subjects with PD-L1 positive tumors.• To determine the overall response rate (ORR) based on RECIST v.1.1.• To determine the ORR based on RECIST v.1.1 in subjects with PD-L1 positive tumors.• To determine the duration of response (DoR) based on RECIST v.1.1.• To determine the DoR based on RECIST v.1.1 in subjects with PD-L1 positive tumors.• To assess the safety and tolerability of MK3475 (pembrolizumab) in combination with eribulin according to the US National Cancer Institute (NCI) Common Terminology Criteria for Adverse Events (CTCAE) version 4.0.3.
--	---------------------------------------------------------------------------------------------------------------------------------------------------------------------------------------------------------------------------------------------------------------------------------------------------------------------------------------------------------------------------------------------------------------------------------------------------------------------------------------------------------------------------------------------------------------------------------------------------------------------------------------------------------------------------------------------------------------------------------------------------------------------------------------------------------------------------------------------------------------------------------------------------------------------------------------------------------------------------------------------------------------------------------------------------------------------------------------------------------------

Exploratory objectives:

	  
	          
Design	Multicenter, open-label, phase II clinical trial.
Primary endpoint	The primary endpoint of this study is to assess the CBR based on RECIST v.1.1.
Study population and total number of subjects	Female patients age \geq 18 years with advanced HR-positive/HER2-negative breast cancer previously treated with anthracyclines and taxanes. A total of 44 patients will be enrolled into this trial.
Approximate duration of subject participation	All eligible patients will be treated with MK3475 (pembrolizumab) 200 mg on day 1 of each 21-day cycle and eribulin 1.23 mg/m ² (equivalent to eribulin mesylate at 1.4 mg/m ²) on days 1 and 8 of every 21-day cycle. Treatment with MK3475 (pembrolizumab) and eribulin will continue based on physician criteria. No maximum duration of treatment is specified. Study follow-up will be performed 12 months after last study dose.
Calendar and estimated completion dates	Recruitment period is planned to be opened for 11 months. The end of study will be 12 months after last study dose or progressive disease experienced in all patients or when the

	
trial is terminated by the Sponsor, whichever is earlier. This data point will be considered:
 
• End of Recruitment (LPI) (11 months): August 2018• Last Patient Last Visit (LPLV): August 2019• Final Study Report: December 2019

PD-L1:	Programmed cell Death 1-Ligand.
PFS:	Progression Free Survival.
PR:	Partial Response.
PR:	Progesterone Receptor.
PT:	Preferred Term.
Q1:	First quartile.
Q3:	Third quartile.
RECIST:	Response Criteria In Solid Tumors.
SD:	Stable Disease.
SDev:	Standard Deviation.
SAE:	Serious Adverse Event.
SOC:	System Organ Class.

4. Study objectives and variables

4.1 Primary objective(s) and primary variable(s)

Primary objective:

To assess the efficacy -as determined by the CBR (total number of objective responses plus stable disease for at least 24 weeks) based on RECIST v.1.1- of MK3475 (pembrolizumab) in combination with eribulin in patients with HR-positive/HER2-negative MBC who have previously received an anthracycline and a taxane (for either early or advanced disease), unless contraindicated, and between one to two lines of chemotherapy in the metastatic setting.

Primary endpoint:

To determine the CBR based on RECIST v.1.1.

4.2 Secondary objective(s) and secondary variables

Secondary objectives:

- To determine the CBR based on RECIST v.1.1 in subjects with PD-L1 positive tumors.
- To determine the PFS based on RECIST v.1.1.
- To determine the PFS based on RECIST v.1.1 in subjects with PD-L1 positive tumors.
- To determine the OS (OS will be collected at the end of the study).
- To determine the OS in subjects with PD-L1 positive tumors.
- To determine the ORR based on RECIST v.1.1.
- To determine the ORR based on RECIST v.1.1 in subjects with PD-L1 positive tumors.
- To determine the DoR based on RECIST v.1.1.
- To determine the DoR based on RECIST v.1.1 in subjects with PD-L1 positive tumors.
- To assess the safety and tolerability of MK3475 (pembrolizumab) in combination with eribulin according to the US National Cancer Institute (NCI) Common Terminology Criteria for Adverse Events (CTCAE) version 4.0.3.

Secondary endpoints:

- CBR based on RECIST v.1.1 in subjects with PD-L1 positive tumors.
- PFS based on RECIST v.1.1.
- PFS based on RECIST v.1.1 in subjects with PD-L1 positive tumors.
- OS (OS will be collected at the end of the study).
- OS in subjects with PD-L1 positive tumors.
- ORR based on RECIST v.1.1.
- ORR based on RECIST v.1.1 in subjects with PD-L1 positive tumors.
- DoR based on RECIST v.1.1.
- DoR based on RECIST v.1.1 in subjects with PD-L1 positive tumors.
- Safety.

4.3 Exploratory objective(s) and exploratory variables

Exploratory objectives:

Exploratory endpoints:

Experior will send a list of protocol deviations (major and minor) to establish the per-protocol set after the close out of data base (see section 5.1).

Intent-to-treat (ITT) set with PD-L1 positive tumors

ITT set will include all patients with PD-L1 positive tumors that accomplish selection criteria and receive at least one drug exposure.

Safety set

The safety set includes patients who receive at least one dose of study medication.

5.1 Protocol deviations

Major deviation is defined as a breach that may significantly affect the safety and rights of the trial subjects or the reliability and robustness of the data generated in the clinical trial.

Minor deviation is defined as conditions, practices or processes that indicate a need for improvement but are not expected to harm the rights, safety or well-being of the patients and/or the quality of the data.

Listings of protocol deviations will be reviewed prior to database lock and them will be send to sponsor in the closeout phase.

To determine per protocol set, all major protocol deviations will be checked, and a list of exclude patients of the statistical analysis will be established by the Steering Committee.

Data Management unit will review the following protocol deviations according to the data registered in the eCRF:

- Inclusion/exclusion criteria not met.
- Tumor assessments out of window (according to the protocol).
- Visits out of window (according to the protocol).
- Specific evaluations (ECOG, vital signs, hematology, etc.) not performed.
- Prohibited medication administered.
- Adjustments of dose not performed according to the protocol.
- Study treatment interruptions > 21 days.
- Study treatment administration out of window.

Furthermore, Project Manager/CRA will provide a list of major protocol deviations registered during the monitoring visits period.

6. Statistical strategy

Below are detailed the statistical aspects of the data analysis.

6.1 Primary analysis

Primary analysis will be based primarily on the Full analysis set and secondarily on the Per protocol analysis set (if applicable, see section 5).

6.1.1 Summary statistics

CBR is defined as the number of subjects with complete response (CR), partial response (PR) or stable disease (SD) for at least 24 weeks divided by the number of patients in the analysis set.

$$\text{CBR} = (\text{CR} + \text{PR} + \text{SD}) / \text{Total number of patients}$$

The CBR results will be presented as number and proportion of patients with clinical benefit and 95% CI of the proportion.

6.1.2 Statistical inference

- The study will be declared positive in the analysis of CBR if the one-sided p-value estimated in accordance with exact binomial test is ≤ 0.05 . With this criterion, we will reach a positive finding if ≥ 17 patients achieve a clinical benefit among 39 patients.
- With this design, there is an 80% power of a positive finding if the true CBR is $\geq 50\%$. The one-sided type I error is 0.05.

6.2 Secondary analysis

Secondary analysis will be performed on full analysis and per-protocol sets. Safety objectives will be based on the safety set. ITT set will be used to analyze the objectives based in subjects with PD-L1 positive tumors.

6.2.1 Summary statistics

Efficacy:

- CBR is defined as the number of subjects with complete response (CR), partial response (PR) or stable disease (SD) for at least 24 weeks based on RECIST v.1.1 divided by the number of patients in the analysis set (in subjects with PD-L1 positive tumors). Tumor response will be defined as best response. The CBR results will be presented as number and proportion of patients with clinical benefit and 95% CI of the proportion.
- The radiological PFS is defined as the time from the first dose of treatment until death by any cause or objective tumor progression according to RECIST v.1.1. Patients with

EudraCT number: 2016-004513-27

no progression or death will be censored at the date of their last evaluable imaging.

PFS censoring rules will follow FDA guidance in 2007 (see Table 1 - Appendix I).

- The first dose of treatment is defined as the minimum date of the first administration of eribulin and/or pembrolizumab.
- The PFS as assessed by investigator is defined as the time from the first dose of treatment until death by any cause or objective tumor progression as assessed by investigator according to RECIST v.1.1. Patients with no progression or death will be censored at the date of their last evaluable imaging. PFS censoring rules will follow FDA guidance in 2007 (see Table 2- Appendix I).
 - The first dose of treatment is defined as the minimum date of the first administration of eribulin and/or pembrolizumab.
- The OS is defined as the time from the first dose of treatment until death by any cause or the last date the patient was known to be alive. Patients who are lost to follow-up and the patients who are alive at the date of data cut-off will be censored at the date the patient was last known alive (censoring rules are specified in Table 3 - Appendix I).

A Kaplan-Meier survival analysis will be carried out to analyse PFS and OS. Number of events, median survival time and the corresponding 95% CI will be provided. Survival curves will be reported.

- The ORR is defined as the number of patients with CR and PR divided by the number of patients in the analysis population. Tumor response will be defined as best response, based on local investigator's assessment according to RECIST v.1.1. ORR will be reported as a proportion with the corresponding 95% CI.
- The DoR is defined as the time from first documented CR or PR until disease progression or death from any cause, according to RECIST v.1.1. In case of the patient first reaching PR and later CR, the duration of CR will be measured and reported separately, starting from the date when first documented and ending when a progressive disease is diagnosed, or the patient dies.

Patients without PD or death will be censored and patients who have not documented neither CR nor PR response will be considered as not available in the Kaplan Meier analysis.

Number of events, median survival time, 95% CI of median and survival curves calculated with Kaplan Meier analysis will be provided.

Safety:

EudraCT number: 2016-004513-27

- The degree of exposure (dose, duration of treatment, number of patients) will be assessed to determine the degree to which study safety can be assessed. These results will be presented with descriptive statistics (n, NA, mean, standard deviation, median and range).
- Adverse events (AEs) and serious AEs (SAEs) will be classified using the Medical Dictionary for Regulatory Activities (MedDRA). AEs will be presented by preferred term (PT) and by system organ class (SOC). Severity, relationship to study drug (eribulin and pembrolizumab), action taken and outcome will be reported as frequency tables.
- Concomitant medications will be coded to the appropriate Anatomical-Therapeutic-Chemical (ATC) code indicating 1st to 4th levels. The results will be reported by frequency tables.
- Deaths and study discontinuations will be described and assessed. It will be reported by frequency tables.

6.2.2 ***Statistical inference***

A Kaplan-Meier survival analysis will be performed to analyze PFS, OS and DoR. The number of events and the median survival time with corresponding 95% CI will be provided.

1- and 2-year survival rates with corresponding 95%CI will be calculated.

Comparisons using log rank test or model of Cox proportional hazards multivariate analysis will be used if needed, and P values of 0.05 or less will be considered to indicate statistical significance.

6.3 ***Exploratory analysis***

6.3.1 ***Summary statistics***

6.4 ***Subgroup analysis***

Subgroup analysis for CBR, ORR, PFS, OS and DoR will be performed outside the indications of the study protocol. The following variables will be part of this analysis to explore differences between subgroups of subjects:

- Ki67 ranges ($\leq 13\%$ (low), 14-19% (medium), $\geq 20\%$ (high))
- Previous treatment with CDK4/6 inhibitor
- Previous treatment with PI3K inhibitor

The next variables will be used for the PFS, CBR and ORR subgroup analysis:

- Previous treatment with mTOR inhibitor
- ECOG (0 vs. 1)
- Number of organs involved (< 3 organs vs. ≥ 3 organs)
- Number of chemotherapy lines in metastatic setting (1 line vs. 2 lines)
- Endocrine sensitivity. Defined according to either of the following criteria:
 - Relapse that occurred after at least 24 months while the patient was receiving adjuvant endocrine therapy.
 - Progression that occurred after at least 24 weeks while the patient was receiving endocrine therapy in the context of metastatic disease.
- Neutrophil/Lymphocyte, ratio (<3 vs ≥ 3)

6.5 **Statistical methods**

6.6 **Safety analysis**

The safety analysis has been included in secondary analysis (see 6.2.1).

6.7 **Demographic and baseline characteristics**

Demographic and baseline characteristics will be analyzed using the full analysis set.

Descriptive statistics will use for the analysis: continuous variables will be summarized as n, number of not available data (NA), mean, standard deviation (SDev), median, first and third quartiles, minimum and maximum values. For categorical variables frequency tables will be presented (n and %).

Demographic and baseline variables are:

- Age (at the IC signature)
- Race
- Clinically significant disease and surgical interventions (they will be coded with MedDRA)
- Toxic habits
- History of cancer
 - Number of relapses
 - Hormone receptors: ER and PR values
 - Ki67
 - HER2 status
 - Patients treated with anthracyclines, taxanes and antihormone therapy.

- Previous antineoplastic treatment for breast cancer. They will be classified as:
 - Chemotherapy: Antracycline, Taxanes, Capecitabine, Vinorelbine, Other
 - Endocrine therapy: Tamoxifen, Aromatase Inhibitors, Fulvestrant.
 - Target therapy: CDK4/6 inhibitors, ParP inhibitors, mTOR inhibitors.
- Previous procedure for breast cancer (surgery/radiotherapy).
- HIV, HBV, HCV serology.
- Physical examination and ECOG status.
- Vital signs / ECG / LVEF.
- Hematology and coagulation.
- Biochemistry and thyroid function.
- Evolution tables will be presented for laboratory values (hematology, biochemistry, coagulation, thyroid function). Data will be summarized with descriptive statistics for baseline and post-dose values.
- Frequencies for toxicities related to clinically significant laboratory values will be presented (for 2-5 CTCAE grades).

6.8 ***Statistical model assumptions***

The proportional hazards assumption in the Cox model will be checked.

6.9 ***Transformation of expected variables***

- The CBR is defined as the proportion of subjects who have best overall response of CR, PR or SD (by RECIST v.1.1):

$$\text{CBR} = (\text{CR} + \text{PR} + \text{SD}) / \text{Total of subjects}$$

- The ORR is defined as the proportion of subjects who have best overall response of CR or PR (by RECIST v.1.1):

$$\text{ORR} = (\text{CR} + \text{PR}) / \text{Total of subjects}$$

- The time to progression is defined as the difference between start of study drug (C1D1) and the progression date or death (whichever occurs first) or the last tumor assessment documented.

- The time to death is defined as the difference between start of study drug and the date of death.
- Duration of response (DoR) is defined as the difference between first documented CR or PR and the disease progression date (by RECIST v.1.1) or death.
- Duration of treatment is defined as the difference between the first dose administrated of study drug (eribulin and/or pembrolizumab) and the date of EOT visit. If no date of EOT is available, the last administration of study drug will be used.

6.10 *Handling of missing data*

There is no planned procedure of imputation of missing values in other variables. The analysis will be performed with the available data.

6.11 *Description of the softwares to be used for data analysis*

Statistical programming and analyses will be performed using the R statistical software version 3.1.3.

6.12 *Interim analysis protocol*

No interim analysis is planned.

6.13 *List of tables and figures*

The tables below are an approximated list of the tables and figures that will be shown in the statistical analysis. They will be able to modify as required.

List of tables:

Descriptive statistics for the age at the informed consent signature

Absolute and relative (%) frequencies for the race

Absolute and relative (%) frequencies for significant disease and surgical intervention (registered in medical history).

Absolute and relative (%) frequencies for toxic habits

Descriptive statistics for number of relapses

Absolute and relative (%) frequencies for hormonal receptors (ER, PR) and HER2 status

Descriptive statistics for Ki67

Absolute and relative (%) frequencies for patients treated with anthracyclines, taxanes and antihormone therapy (previous treatments)

Absolute and relative (%) frequencies for patients treated with chemotherapy, endocrine therapy and target therapy.

Absolute and relative (%) frequencies for previous procedure for breast cancer (surgery/radiotherapy)

Absolute and relative (%) frequencies for HIV, HBV HCV

Absolute and relative (%) frequencies for physical examination and ECOG status at screening visit

Descriptive statistics for vital signs, ECG and LVEF at screening visit

Descriptive statistics for laboratory tests (hematology, biochemistry and thyroid function)

Absolute and relative (%) frequencies for toxicities (2 to 5 CTCAE grades) related to clinically significant laboratory values

Absolute and relative (%) frequencies for the best response according to RECIST v1.1 criteria.

Results of CBR (proportion, % and 95% CI)

Results for CBR vs. Ki67 ranges

EudraCT number: 2016-004513-27

Results for CBR vs. previous treatment with CDK4/6 inhibitor

Results for CBR vs. previous treatment with PI3K inhibitor

Results for CBR vs. previous treatment with mTOR inhibitor

Results for CBR vs. PD-L1

Results for CBR vs. ECOG

Results for CBR vs. number of organs involved

Results for CBR vs. lines of chemotherapy in metastatic setting

Results for CBR vs. endocrine sensitivity

Results for CBR vs. Neutrophil/Lymphocyte, ratio (<3 vs >=3)

Absolute and relative (%) frequencies for progression disease events and/or deaths

Descriptive statistics for PFS (according to RECIST v1.1 criteria)

Results for PFS (according to RECIST v1.1 criteria) vs. Ki67 ranges

Results for PFS (according to RECIST v1.1 criteria) vs. previous treatment with CDK4/6 inhibitor

Results for PFS (according to RECIST v1.1 criteria) vs. previous treatment with PI3K inhibitor

Results for PFS (according to RECIST v1.1 criteria) vs. previous treatment with mTOR inhibitor

Results for PFS (according to RECIST v1.1 criteria) vs. PD-L1

Results for PFS (according to RECIST v1.1 criteria) vs. ECOG

Results for PFS (according to RECIST v1.1 criteria) vs. number of organs involved

Results for PFS (according to RECIST v1.1 criteria) vs. lines of chemotherapy in metastatic setting

Results for PFS (according to RECIST v1.1 criteria) vs. endocrine sensitivity

Results for PFS (according to RECIST v1.1 criteria) vs. Neutrophil/Lymphocyte, ratio (<3 vs >=3)

Descriptive statistics for PFS (according to investigator criteria)

Results for PFS (according to investigator criteria) vs. Ki67 ranges

Results for PFS (according to investigator criteria) vs. previous treatment with CDK4/6 inhibitor

Results for PFS (according to investigator criteria) vs. previous treatment with PI3K inhibitor

Results for PFS (according to investigator criteria) vs. previous treatment with mTOR inhibitor

Results for PFS (according to investigator criteria) vs. PD-L1

Results for PFS (according to investigator criteria) vs. ECOG

Results for PFS (according to investigator criteria) vs. number of organs involved

Results for PFS (according to investigator criteria) vs. lines of chemotherapy in metastatic setting

Results for PFS (according to investigator criteria) vs. endocrine sensitivity

Results for PFS (according to investigator criteria) vs. Neutrophil/Lymphocyte, ratio (<3 vs ≥ 3)

Descriptive statistics for PFS (according to irRECIST v1.1 criteria)

Descriptive statistics for OS

Results for OS vs. Ki67 ranges

Results for OS vs. previous treatment with CDK4/6 inhibitor

Results for OS vs. previous treatment with PI3K inhibitor

Results for OS vs. PD-L1

Results of ORR (proportion, % and 95% CI) (according to RECIST v1.1 criteria)

Results for ORR vs. Ki67 ranges

Results for ORR vs. previous treatment with CDK4/6 inhibitor

Results for ORR vs. previous treatment with PI3K inhibitor

Results for ORR vs. previous treatment with mTOR inhibitor

Results for ORR vs. PD-L1

Results for ORR vs. ECOG

Results for ORR vs. number of organs involved

Results for ORR vs. lines of chemotherapy in metastatic setting

Results for ORR vs. endocrine sensitivity

Results for ORR vs. Neutrophil/Lymphocyte, ratio (<3 vs ≥ 3)

Results of ORR (proportion, % and 95% CI) (according to irRECIST v1.1 criteria)

Descriptive statistics for DoR

Results for DoR vs. Ki67 ranges

Results for DoR vs. previous treatment with CDK4/6 inhibitor

Results for DoR vs. previous treatment with PI3K inhibitor

Results for DoR vs. PD-L1

Descriptive statistics for dose of study treatment

Descriptive statistics for duration of treatment

Absolute and relative (%) frequencies for adverse events (coded as PT and SOC terms from MedDRA): severity, relationship to study drugs, action taken and outcome

Absolute and relative (%) frequencies for concomitant medication (coded using ATC)

Absolute and relative (%) frequencies for deaths and discontinuations

List of figures

Kaplan-Meier curves for PFS (according to RECIST v1.1 criteria) and subgroups

Kaplan-Meier curves for PFS (according to investigator criteria) and subgroups

Kaplan-Meier curves for PFS (according to irRECIST v1.1 criteria)

Kaplan-Meier curves for OS and subgroups

Kaplan-Meier curves for DoR and subgroups

7. References

1. R Core Team (2015). R: A language and environment for statistical computing. R Foundation for Statistical Computing, Vienna, Austria. URL (<http://www.R-project.org/>).
2. Guidance for Industry: Clinical Trail Endpoints the Approval of Cancer Drugs and Biologics (May 2007).

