1.3.2 Phase II trials

Several phase II studies have assessed the antitumor activity of eribulin in heavily pretreated MBC patients. The first study (study 201) was published by Vahdat et al. who investigated the efficacy and safety of eribulin in 103 patients with MBC who had received prior treatment with an anthracycline and taxanes [12]. Based on the results of previous phase I studies, eribulin mesylate 1.4 mg/m^2 was initially administered as a 2–5-minute intravenous (IV) infusion on days 1, 8, and 15 of a 28-day cycle. After an assessment of tolerability data, which indicated that many patients were experiencing severe neutropenia on day 15, a protocol amendment was made, and a second group of patients received eribulin mesylate 1.4 mg/m^2 administered as an IV infusion over 2 to 5 minutes on days 1 and 8 of a 21-day cycle. In this study, eribulin demonstrated in the per-protocol set ($n = 87$) an overall response rate (ORR) by independent review of 11.5% (95% confidence

interval [CI], 5.7–20.1, all partial responses) and achieved a clinical benefit rate (CBR) of 17.2% (95%CI, 10.0–26.8). The median duration of response (DoR), median progression-free survival (PFS), and median OS were 5.6 months (95%CI, 1.4–11.9), 2.6 months (95%CI, 0.03–14.9), and 9 months (95%CI, 0.5–27.2), respectively.

In the second phase II study (study 211), reported by Cortes et al., a total of 291 patients with locally advanced disease or MBC who had received prior treatment with anthracyclines, taxanes, and capecitabine were included [13]. The patients received eribulin mesylate 1.4 mg/m² as a 2–5-minute IV infusion on days 1 and 8 of a 21-day cycle. In this study, eribulin showed an ORR by independent review of 9.3% (95%CI, 6.1–13.4, all partial responses) and a CBR of 17.1% (95%CI, 12.8–22.1). The median DoR, median PFS, and median OS were 4.1 months (95%CI, 1.4–11.9), 2.6 months (95%CI, 0.03–13.1), and 10.4 months (95%CI, 0.6–19.9), respectively.

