Finally, in other phase II trial, reported by Aogi et al., the safety and efficacy of eribulin was investigated in 80 Japanese patients with MBC who had previously been treated with an anthracycline and a taxane [14]. The study used the same dosing regimen and mode of administration as that of the study by Cortes et al. In this study, eribulin demonstrated an ORR by independent review of 21.3% (95%CI, 12.9–31.8, all partial responses) and a CBR of 27.5% (95%CI, 18.1–38.6). The median DoR, median PFS, and median OS were 3.9 months (95%CI, 2.8–4.9), 3.7 months (95%CI, range 2–4.4), and 11.1 months (95%CI, range 7.9–15.8), respectively.

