8.2 Statistical plan

8.2.1 Primary efficacy endpoint

The primary endpoint is to evaluate the CBR. The CBR is defined as the number of patients with complete response, partial response, or stable disease for at least 24 weeks divided by the number of patients in the analysis set. Tumor response will be assessed every nine weeks for the first 12 months following first dose of study treatment, and every 12 weeks thereafter. Tumor response will be defined as best response, based on local Investigator's assessment according to the RECIST criteria v.1.1.

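### SAP 6.9 derives the primary endpoint, CBR, with stable disease of any duration, while the rest of the plan requires at least 24 weeks

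*SAP*

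**What the plan says.** Most of the plan defines CBR in one way. The primary objective in SAP 4.1 (and protocol 2.1 and both synopses) describes it as "total number of objective responses plus stable disease for at least 24 weeks". The text of SAP 6.1.1, which specifies the primary analysis, counts complete response (CR), partial response (PR) or "stable disease (SD) for at least 24 weeks divided by the number of patients in the analysis set". SAP 6.2.1 uses the same condition for PD-L1-positive patients, and protocol 8.2.1 has "stable disease for at least 24 weeks divided by the number of patients in the analysis set".

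SAP 6.9 (Transformation of expected variables) defines the same variable differently: "The CBR is defined as the proportion of subjects who have best overall response of CR, PR or SD (by RECIST v.1.1"). Its formula is (CR + PR + SD) / Total of subjects. It gives no minimum duration and does not refer back to 6.1.1. The formula printed under the 6.1.1 text also shows SD without a duration.

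The success rule, in SAP 6.1.2 and protocol 8.2.7, is a one-sided exact binomial p-value of at most 0.05, which the plan equates to at least "17 patients achieve a clinical benefit among 39 patients". The sample size sections (SAP 4.5, protocol 8.1) give the unacceptable rate as 30% and the successful rate as 50%.

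**The concern.** Two definitions of the only endpoint with a success rule stand in the same SAP, and no text ranks them. Section 6.9 is where CBR, ORR, time to progression, duration of response and duration of treatment are turned into analysis variables, so a programmer could reasonably build from it.

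The two versions measure different things. Scans are every nine weeks in the first year. A patient with SD at week 9 and progression at week 18 counts as a success under 6.9 and as a failure under 6.1.1. The 30% and 50% rates were set for CBR, which the objectives define with 24-week SD. Testing plain CR+PR+SD against 30% sets a disease control rate against a benchmark for longer benefit, and the stated 0.05 type I error would no longer hold. Two competent programmers could reach opposite go/no-go conclusions from the same data, and a choice made after seeing the data would be hard to defend.

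**Working it through.** **1. Inputs.** From SAP 4.5 and 6.1.2 (protocol 8.1 and 8.2.7): p0 = 0.30, p1 = 0.50, one-sided alpha 0.05, power 80%, cut-off 17 of 39, drop-out 10%, 44 patients enrolled. From protocol 8.2.1: scans every nine weeks for 12 months.

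**2. The plan's own design.** With X ~ Binomial(39, p):

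- P(X ≥ 17 | 0.30) = 0.04998
- P(X ≥ 17 | 0.50) = 0.832
- P(X ≥ 16 | 0.30) = 0.094, so 17 is the smallest valid cut-off
- 39 / (1 − 0.10) = 43.3, rounded up to 44

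The design reproduces for the 24-week endpoint. Power exceeds the 80% target because the binomial is discrete.

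**3. Effect of a literal 6.9, without a time-to-event model.** Let s be the share of patients whose best response is SD lasting less than 24 weeks. If the true 24-week CBR is at the null, the 6.9 rate is 0.30 + s. The documents give no value for s, so it is varied. The last column shows all 44 patients analysed, with the exact cut-off of 19 (type I error 0.044).

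| s (assumed) | 6.9 rate | P(≥17 of 39) | P(≥19 of 44) |
|---|---|---|---|
| 0 | 0.30 | 0.050 | 0.044 |
| 0.05 | 0.35 | 0.169 | 0.163 |
| 0.10 | 0.40 | 0.381 | 0.387 |
| 0.15 | 0.45 | 0.630 | 0.651 |
| 0.20 | 0.50 | 0.832 | 0.854 |
| 0.30 | 0.60 | 0.987 | 0.992 |

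**4. How large s might be, from the protocol's background.** Protocol 1.3.2 and 1.3.3 quote median PFS on eribulin alone of 2.6 to 4.1 months. Multiplying by 30.44/7 gives 11.3 to 17.8 weeks, all later than the week-9 scan and its +7-day window. At least half of those patients were therefore progression-free at week 9, while the phase II CBRs quoted in 1.3.2 run from 17.1% to 27.5%. A 6.9-type rate of 0.50 gives P(positive) = 0.83. If 10% have no usable scan, 0.50 × 0.9 = 0.45 gives 0.63. These are other populations, so this is an illustration.

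**5. Assumed model.** Let r be the responder share, counted whatever the duration. Non-responders have Weibull progression times with shape k, fixed so that the true 24-week CBR is 30%:

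- S(24) = (0.30 − r) / (1 − r)
- S(9) = S(24)^((9/24)^k)
- 6.9 rate = r + (1 − r) × S(9)

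Example with r = 0.20 and k = 0.8: S(24) = 0.10/0.80 = 0.125, S(9) = 0.387, rate = 0.20 + 0.80 × 0.387 = 0.510, and P(≥17 of 39) = 0.861.

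| r | k | 6.9 rate | P(≥17 of 39) |
|---|---|---|---|
| 0.09 | 0.8 | 0.556 | 0.952 |
| 0.09 | 1.5 | 0.740 | >0.999 |
| 0.20 | 0.8 | 0.510 | 0.861 |
| 0.20 | 1.5 | 0.696 | >0.999 |
| 0.213 | 0.8 | 0.501 | 0.835 |
| 0.25 | 0.8 | 0.468 | 0.71 |
| 0.28 | 0.8 | 0.420 | 0.48 |

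The value r = 0.213 is the highest phase II eribulin ORR quoted in protocol 1.3.2.

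**The case against.** The best defence is that the intended definition is clear. The 24-week condition appears in both synopses, both primary objectives, protocol 6.4.2 and 8.2.1, and the SAP's primary-analysis section. SAP 6.1.1 prints the bare formula directly beneath a sentence that requires 24 weeks, so an unqualified SD in a formula may be shorthand. Where the SAP knowingly departs from the protocol, as in its subgroup section, it says so, and 6.9 carries no such statement. This is probably a drafting omission. But in 6.9 the sentence as well as the formula lacks the duration, the section is a derivation specification, and no text sends the reader elsewhere. Probable intent does not settle what will be programmed.

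The objection to the modelled figures is partly right. They fall as the responder share rises: 0.71 at r = 0.25 and 0.48 at r = 0.28, with shape 0.8. The only quoted data on this combination, in triple-negative disease (protocol 1.11), show ORR 33.3% and CBR 41%, so most of the benefit there was response. If 10% of patients have no usable scan, the case r = 0.20, k = 0.8 drops from 0.86 to 0.67. The protocol also does not say what SD duration the quoted phase II CBRs used. The conclusion should therefore rest on the text and the table in step 3. Every case considered still exceeds 0.05.

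Protocol 6.4.2 is loosely worded and could be read as applying the 24 weeks to CR and PR too. That is a separate ambiguity; it still keeps a 24-week minimum and does not support 6.9.

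**Conclusion.** The concern holds, and the point must be fixed before analysis. The contradiction lies in the wording of the primary endpoint and depends on no calculation. If 6.1.1 is followed, the test performs as planned (type I error 0.050, power 0.83). If 6.9 is followed as written, the type I error is not controlled for the 24-week endpoint: 5 percentage points of short SD more than triple it to 0.17, and 20 points take it to 0.83. The exact inflation is unknown because the documents give no rate of SD shorter than 24 weeks in this population. The figures assume a true 24-week CBR of exactly 30%. The Weibull results also depend on the assumed responder share, shape and scan completeness.

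**What to change.** In SAP 6.9, replace SD with SD for at least 24 weeks in the CBR sentence and formula, and make the same change in the formula under 6.1.1. CBR then reads (CR + PR + SD ≥ 24 weeks) / all patients in the analysis set in every section, matching the 6.1.1 text and protocol 8.2.1. If the plain CR+PR+SD rate is of interest, report it separately as a disease control rate, without the 17/39 rule.

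The cost is a few words in the SAP. The reported CBR will be lower than the 6.9 formula would give if any patient's best response is shorter SD. The sample size, the decision rule and the planned power do not change. How 24-week SD is established on a nine-week scan grid is a separate clarification for the sponsor, outside this change.
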